7.12 Pre-Surgical Evaluation

The pre-surgical evaluation will consist of a central review of each subject's epilepsy history, MRI, EEG and any additional testing results available (e.g., PET, SPECT, invasive EEG or MEG) to confirm study qualification for the Visualase procedure.

Following consent, the site will enter subject data obtained during screening into the electronic database. The following data are specifically required for the pre-surgical evaluation for every enrolled subject (unless withdrawn prior to pre-surgical evaluation):

- MRI
 - T1- and T2-weighted images including thin section coronal images suitable for quantitative measurement, sufficient to confirm eligibility criteria
 - MRI report
- Video EEG
 - Printout of seizure activity from EEG
 - o EEG report and video description
- Additional testing, if performed (e.g., PET, SPECT, invasive EEG or MEG)
- Epilepsy History and Seizure Classification Forms

Each subject's data are reviewed by a central committee (Appendix B) to verify study qualification for the Visualase procedure based on the following criteria:

- Does the submitted MRI show mesial temporal atrophy accompanied by either increased signal indicative of gliosis or by loss of internal architecture in the hippocampus?
- Does the EEG evidence show seizures from one temporal lobe consistent with MTLE?
- Is the seizure semiology consistent with MTLE?
- Based on the MRI, EEG and semiology, is the laterality consistent?
- If additional testing has been performed (e.g., PET, SPECT, invasive EEG or MEG), is it discordant from the seizure focus scheduled for ablation?

Each subject's data review will be assigned to one of the Committee members based on availability. The assigned Committee member may consult with others, though the assigned Committee member is individually responsible for making an evaluation decision. Committee members who also act as study investigators may not evaluate subjects enrolled by their own institution. The assigned Committee member will approve, disapprove or defer the subject's continued participation in the trial.

Subjects who are being considered for retreatment with another Visualase procedure (per Section 7.17) are evaluated by the committee per the same workflow as described above, though the supportive evidence requirements and verification criteria are determined on a case-by-case basis by the assigned Committee member (i.e., they are not pre-specified).

7.13 Baseline Visit

At any time after enrollment, but before the Visualase procedure, subjects will have a Baseline Visit to perform assessments that serve as a comparison to post Visualase procedure assessments. If needed, the Baseline Visit may be performed on multiple days, provided that all assessments are completed prior to the Visualase procedure.

The following activities are to be performed at this visit:

- Review and documentation of current AEDs and concomitant psychotropic medications
 - AEDs and dosages must remain stable for at least 30 days prior to the Visualase procedure
- Neurological exam, including oculomotor nerves and confrontation visual field test
- AE assessment
- Neurocognitive assessments, administered by qualified study personnel:
 - Boston Naming Test
 - Controlled Oral Word Association Test (COWA) (FAS)
 - Emory Semantic Fluency Tasks
 - Emory Famous Faces Naming/Recognition
 - Rey Auditory Verbal Learning Test, Form A
 - Wechsler Memory Scale (WMS-IV) Visual Reproduction Test
 - Wechsler Memory Scale (WMS-IV) Verbal Paired Associates

- Mood and Quality of Life (QOL) surveys, completed by the subject:
 - Beck Depression Inventory II
 - Beck Anxiety Inventory
 - Quality of Life in Epilepsy Inventory (QOLIE-31)
 - SF-36 Health Survey (SF-36)
 - Seizure Severity Questionnaire (SSQ) Version 3
- If available, seizure diary review and documentation of all seizures; a new diary may be given to subject to record future seizures
- Classification of any new types of seizures reported
- Research MRI scan per Section 7.6
 - MRI scans done within 12 months prior to enrollment and performed per Section 7.6 may be used for baseline.
- Assessment of driving and employment/school status
- Neuro-ophthalmologic exam (does not apply to subjects who have undergone the Visualase procedure prior to release of CIP 4.0)
 - Neuro-ophthalmologic exams performed within 12 months prior to enrollment and performed per Section 7.7 may be used for baseline

Results of neurological exams and neurocognitive assessments performed within 12 months prior to enrollment may be used for baseline.

7.14 Study Intervention: Visualase Procedure

The following activities are to be performed before the Visualase procedure:

- AEDs and dosages must remain stable for 30 days prior to the Visualase procedure.
- For females of childbearing potential, a repeat pregnancy test should be done
 within 7 days prior to the Visualase procedure to confirm the subject is still
 eligible. If the pregnancy test is positive, the subject is considered a screen
 failure and is exited from the study.

The following activities are to be performed prior to discharge:

- Visualase procedure
- MRI scans before, during and after the Visualase procedure (per Section 7.6)
- Review and documentation of current AEDs and concomitant psychotropic medications
- AE assessment
- Healthcare services utilization assessment
- If available, review of seizure diary and documentation of all seizures; new diary may be given to subject to record any future seizures
- Classification of any new seizure types reported
- Pain scale completed after the Visualase procedure

The procedure should be performed in accordance with the Instructions for Use (IFU) supplied with the device. A supplemental surgical Technique Recommendations document will be provided to all sites to facilitate consistent use, correct placement and

function of the device, as well as to minimize risk to subjects. The Technique Recommendations should be reviewed by all participating study surgeons and adherence to its guidance is strongly encouraged.

As indicated in the IFU, the potential effect of laser ablation on the stability of gadolinium complexes such as those used in MRI contrast agents (CAs) is currently unknown. Physicians should therefore observe a "washout" interval of at least three (3) half-lives (t½ for the CA being used) between the administration of Gadolinium-based CAs and initiation of the laser ablation.

The subject is positioned and stereotactic registration for intraoperative navigation and cranial access is accomplished. This may require application of a stereotactic head frame or it may be frameless via surface-based registration (e.g., facial tracing) or placement of scalp or bone fiducials. Other appropriate neurosurgical stereotactic modalities may be used in accordance with the manufacturer's instructions. In cases where a head frame is used, imaging studies (CT or MRI) are then obtained and interpreted for usability by the surgeon, for identification of reference points and direct use in operative planning after the images are fused. At the surgeon's discretion, general anesthesia may be induced prior to application of the head frame. For all types of stereotactic registration, planning is performed to identify the precise entry point on the skull as well as to define the target and the safest trajectory through the brain to reach it, as follows. A target point is selected on a coronal MRI slice through the hippocampal head, within the center of the hippocampus from medial-to-lateral as well as dorsalventral (essentially the dentate gyrus). An initial entry point is selected on a coronal MRI slice through the hippocampal body at approximately the level of the lateral mesencephalic sulcus, which again is centered in the middle of the hippocampus. This trajectory is then expanded to the amygdala anteriorly, and to the cortical surface posteriorly. The defined trajectory is then further refined a) to maximize its extent within the hippocampus along its length from the level of the tectal plate to the amgydala; and b) to avoid cerebral vasculature and, if possible, entry into the ventricle. Attention is paid to the location of the optic radiation and thalamus to avoid proximity. Depending on the registration system, trajectory and target testing may be performed on the back table using a phantom.

If not previously performed, general anesthesia is induced. The subject's head is prepped by shaving or parting the hair to achieve a sterile field. If a head frame is used, the stereotactic arc is attached to the existing stereotactic frame and the entry and target coordinates are input. Alternately, for frameless access, the stereotactic arm is mounted onto a skull clamp on the subject's head. The entry point is marked and, following local anesthesia, a scalp incision is performed and a minimally invasive twist drill craniostomy is made through the skull. The dura is then opened, for example using a sequence of sharp and blunt instruments or cautery. The pia is opened using similar techniques. With aid of an alignment rod, the laser anchor bolt is then placed through the twist drill craniostomy and secured into the skull at the correct trajectory.

After measurements associated with the trajectory from bone anchor to target are taken, the laser applicator probe is then advanced to the target site and held in place by the anchor bolt. If using a stereotactic head frame, the arc is then removed. If using frameless registration, the stereotactic arm and skull clamp are removed.

The subject is then prepared for transfer to the MRI suite to localize the laser applicator probe and perform the ablation of the brain tissue. During transfer, the laser application probe and the anchor bolt are managed to ensure the anchor bolt is secure and the

probe is not damaged. Alternately, the procedure may be performed in an MRI-equipped operative suite.

The subject is positioned within the MRI machine, with continued attention to the laser application probe and anchor bolt. An MRI scan is performed and interpreted by the surgeon to localize the laser application probe, confirming that the laser application probe is in the correct position and assessing for any adverse events during insertion or transfer.

The correct ablation parameters (power and duration) are determined by the surgeon. Selected MRI images are transferred to the ablation system and safety set points are identified on the images to define the area of ablation to prevent overheating of adjacent tissues and critical structures. Additional safety set points are placed on the images to monitor for excessive heating at the site of the laser application probe.

A test MRI-guided laser ablation is performed. After the test laser ablation is successfully completed, the MRI-guided laser ablation is performed at a wattage to achieve cell death. During ablation, the surgeon monitors and interprets MRI images superimposed on real-time thermal maps displaying the distribution of the heat, to ensure safety and successful target treatment. Based on the MRI information, it is frequently necessary to reposition the laser application probe several times and repeat the laser ablation.

At the end of the laser ablation surgery, a final gadolinium-enhanced MRI is acquired. The surgeon interprets the image to assess the ablation and confirm the ablation zone.

In the MRI suite or operating room, the laser application probe and the anchor bolt are removed. If a stereotactic head frame or bone fiducials were used, they are removed. The scalp incision site is closed by suture, staple, or glue. The subject is transported to the recovery room.

Procedures aborted prior to skin incision may be rescheduled. Procedures aborted after skin incision may be retreated per Section 7.17. If a procedure is aborted without plans to reschedule a subsequent Visualase procedure, the subject will be followed for the modified intent-to-treat analysis of seizures and AEs.

7.15 Scheduled Follow-up Visits

All follow-up visit windows will be calculated from the date of the Visualase procedure. Should a subject miss a visit or the visit fall outside the pre-specified window, a study deviation must be reported and the original follow-up schedule maintained for subsequent visits.

Data analyses will include follow-up visits, regardless of whether the visit occurs within the window. Therefore, a late visit is preferred over a missed visit. Follow-up visit windows are listed in Table 5 and are based on days post-Visualase procedure.

Table 5: Follow-up Visit Windows

Study Follow up	Window (Calculated days post-procedure)			
Study Follow-up Visit	Window Start (days post- procedure)	Target (days post-procedure)	Window End (days post-procedure)	
Follow-up Visit 1 (14 day)	7	14	21	
Follow-up Visit 2 (3 month)	76	90	104	
Follow-up Visit 3 (6 month)	150	180	210	
Follow-up Visit 4 (12 month)	365	365	410	

7.15.1 Follow-up Visit 1: 14 ± 7 Days Post Visualase Procedure

The following activities are to be performed at this visit:

- Documentation of any changes in AEDs and concomitant psychotropic medications
- Neurological exam, including oculomotor nerves and confrontation visual field test
- AE assessment
- Healthcare services utilization assessment
- Review of seizure diary and documentation of any seizures; new diary may be given to subject to record future seizures
- Seizure classification of any new types of seizures

7.15.2 Follow-up Visit 2: 3 Months (90 ± 14 Days) Post Visualase Procedure

The following activities are to be performed at this visit:

- Documentation of any changes in AEDs and concomitant psychotropic medications
- Neurological exam, including oculomotor nerves and confrontation visual field test
- AE assessment
- Healthcare services utilization assessment
- Review of seizure diary and documentation of any seizures; new diary given to subject to record future seizures
- Seizure classification of any new types of seizures
- Neuro-ophthalmologic exam (for subjects consented to CIP 4.0 prior to Follow-up Visit 2)
 - A neuro-ophthalmologic exam performed after the Visualase procedure but prior to reconsent may be used if it was performed per Section 7.7

7.15.3 Follow-up Visit 3: 6 Months (180 ± 30 Days) Post Visualase Procedure

The following activities are to be performed at this visit:

- Documentation of any changes in AEDs and concomitant psychotropic medications
- Neurological exam, including oculomotor nerves and confrontation visual field test
- AE assessment
- Healthcare services utilization assessment
- Neurocognitive assessments, administered by qualified study personnel:
 - Boston Naming Test
 - Controlled Oral Word Association Test (COWA) (FAS)
 - Emory Semantic Fluency Tasks
 - Emory Famous Faces Naming/Recognition
 - Rey Auditory Verbal Learning Test, Form GE-AB

- Wechsler Memory Scale (WMS-IV) Visual Reproduction Test
- Mood, Quality of Life (QOL) and Seizure Severity surveys, completed by the subject:
 - Beck Depression Inventory II
 - Beck Anxiety Inventory
 - Quality of Life in Epilepsy Inventory (QOLIE-31)
 - o SF-36 Health Survey (SF-36)
 - Seizure Severity Questionnaire (SSQ) Version 3
- Review of seizure diary and documentation of any seizures; new diary given to subject to record future seizures
- Seizure classification of any new types of seizures
- Research MRI scan per Section 7.6
 - Note: the subject must be scanned on the same scanner at the Baseline visit and at the 6-month visit
- Neuro-ophthalmologic exam (for subjects who had an abnormal finding at Followup Visit 2, and for subjects consented to CIP 4.0 after Follow-up Visit 2 but prior to Follow-up Visit 3)
 - A neuro-ophthalmologic exam performed after the Visualase procedure but prior to reconsent may be used if it was performed per Section 7.7

7.15.4 Follow-up Visit 4: 12 Months (365 + 45 Days) Post Visualase Procedure The following activities are to be performed at this visit:

- Review and documentation of current AEDs and concomitant psychotropic medications
- Neurological exam, including oculomotor nerves and confrontation visual field test
- AE assessment
- Healthcare services utilization assessment
- Neurocognitive assessments, administered by qualified study personnel:
 - Boston Naming Test
 - Controlled Oral Word Association Test (COWA) (FAS)
 - Emory Semantic Fluency Tasks
 - Emory Famous Faces Naming/Recognition
 - Rey Auditory Verbal Learning Test, Form A
 - Wechsler Memory Scale (WMS-IV) Visual Reproduction Test
 - Wechsler Memory Scale (WMS-IV) Verbal Paired Associates
- Mood, Quality of Life (QOL) and Seizure Severity surveys completed by the subject:
 - Beck Depression Inventory II
 - Beck Anxiety Inventory
 - Quality of Life in Epilepsy Inventory (QOLIE-31)
 - SF-36 Health Survey (SF-36)

- Seizure Severity Questionnaire (SSQ) Version 3
- Review of seizure diary and documentation of any seizures
- Seizure classification of any new types of seizures
- Assessment of driving and employment/school status
- Neuro-ophthalmologic exam (for subjects who had an unresolved abnormal finding at a previous visit, and for subjects consented to CIP 4.0 after Follow-up Visit 3 but prior to Follow-up Visit 4)
 - A neuro-ophthalmologic exam performed after the Visualase procedure but prior to reconsent may be used if it was performed per Section 7.7

7.15.5 Telephone Follow-up

Any subjects who are unable to return in person for an office visit during the visit window may be contacted by phone as a last resort. This allows for identification of any AEs that have occurred, review of the subject's seizure diary, and documentation of any changes in medications since last contact. In this case, the seizure diary may be sent to the site via email, mail or fax. Details of the conversation (including the date and names of the person who conducted the call and with whom they spoke), and the reason for the inability of the visit to occur must be documented.

NOTE: A telephone follow-up is NOT the preferred method of follow-up, and every attempt should be made to have the subject return to the office for the follow-up visit. AEs that are noted at the time of this follow-up visit will be recorded on an AE CRF. A deviation form must be completed for any missed assessments.

7.16 Unscheduled Follow-up Visits

An unscheduled visit is defined as any visit not required by this study. When an unscheduled follow up visit occurs, the subject must be assessed for adverse events and healthcare utilizations per Section 7.18. AE and Healthcare Services Utilization eCRFs must be completed as appropriate. The following should be completed as possible/necessary at the visit:

- Documentation of any changes in AEDs and concomitant psychotropic medications
- Review of seizure diary and documentation of any seizures; new diary given to subject to record future seizures
- Seizure classification of any new types of seizures

A neuro-ophthalmologic exam should be performed for subjects who experience symptoms of a potential vision-related adverse event following the Visualase procedure. A neuro-ophthalmologic exam performed prior to reconsent to CIP 4.0 may be used, if the exam was performed per Section 7.7.

7.17 Retreatment

Subjects who fail to achieve Engel Class I seizure freedom or whose procedure could not be completed as intended prior to discharge may be evaluated for retreatment. Retreatment is defined as a subsequent Visualase procedure after the subject's discharge following the initial Visualase procedure, to treat MTLE ipsilateral to the initial Visualase procedure and also within the temporal lobe. If it is determined that the ablation of additional tissue within the original target site may improve the outcome, the

justification for retreatment and supporting evidence will be entered on an eCRF and submitted to the Pre-Surgical Evaluation Committee for assessment per Section 7.12. Justification and supporting evidence for consideration of retreatment may include, but is not limited to, EEG demonstrating interictal and ictal discharges from the same temporal lobe, MRI showing no other lesions, same type of seizure behavior and auras, and no evidence of extra-temporal lesions.

If the Pre-Surgical Evaluation Committee disagrees with the recommendation for retreatment, the subject may continue participation in the study per their original follow-up schedule without retreatment. Alternatively, the subject may be withdrawn from the study.

If the committee agrees with the recommendation for retreatment, the subject may be scheduled for an additional Visualase procedure. Retreated subjects will have the same assessments at the same intervals as they would for an initial procedure. The new follow-up visit windows will be calculated based on the date of the retreatment Visualase procedure.

Subjects retreated with Visualase after the subject's discharge from the original Visualase procedure will be considered to have failed the primary efficacy endpoint. However, their data will contribute to specified secondary endpoints.

Subjects who undergo open resection after a Visualase procedure will be considered to have failed the primary efficacy endpoint. Seizure and AE data will be collected per the standard of care for the site.

Subjects who are retreated with Visualase or undergo open resection after a Visualase procedure will be followed for 12 months after the secondary procedure, or until the last enrolled subject completes Follow-up Visit 4 (12 months), whichever occurs first.

All subjects will be assessed for safety for the duration of their participation in this study, regardless of whether they are retreated.

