7.19 Study Exit

A study exit eCRF is required for all subjects. Prior to exiting a subject from the study, it is recommended to follow the subject until all ongoing device-related, anesthesia-related, and/or procedure-related AEs are resolved or unresolved with no further actions planned. Upon exiting from the study, no further study data will be collected and no further study visits will occur for the subject. All data available through the time of the subject's exit will be used for analysis.

Subjects are urged to remain in the study as long as possible but may be exited from the study for any of the following situations:

- Subject has completed follow-up
- Subject lost to follow-up

- Subject death
- Subject did not meet inclusion/exclusion criteria (If ineligibility is discovered after the Visualase procedure, the subject will still be followed through 12 months post procedure.)
- Subject chooses to withdraw (e.g., consent withdrawal, relocation to another geographic location)
- Investigator deems withdrawal necessary (e.g., the subject enrolls in a confounding investigational study, the subject fails to maintain adequate study compliance, or it is medically necessary or in the best interest of the subject)

The following information is required to be documented at study exit:

- Reason for exit
- Date of study exit
- If the subject is determined to be lost to follow-up, details of a minimum of 3 contact attempts via 2 different methods (e.g., email, phone, and/or certified letter) must be recorded.

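### After a one-time ablation, a refused retreatment or poor compliance can still end all follow-up, and the retreatment route selectively loses 12-month data on Engel I failures and incomplete procedures

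*Protocol*

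**What the plan says.** **Retreatment (protocol 7.17).** Entry to the retreatment review is limited: "Subjects who fail to achieve Engel Class I seizure freedom or whose procedure could not be completed as intended prior to discharge may be evaluated". If the committee disagrees, the subject may stay on the original visit schedule. The next sentence gives the other option: "Alternatively, the subject may be withdrawn from the study".

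**Exit (protocol 7.19).** The investigator may exit a subject for several reasons, one being that "the subject fails to maintain adequate study compliance". The consequence of any exit is total: "Upon exiting from the study, no further study data will be collected and no further study visits will occur for the subject". Data up to that point are kept: "All data available through the time of the subject's exit will be used for analysis". Before exit, "it is recommended to follow the subject until all ongoing device-related, anesthesia-related, and/or procedure-related AEs are resolved or unresolved" (the latter once nothing more is to be done). That is a recommendation, although section 10.2.3 words it more strongly.

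**Where follow-up is protected.** Under protocol 7.14, if a procedure is aborted and no further one is planned, "the subject will be followed for the modified intent-to-treat analysis of seizures and AEs". Section 7.19 itself keeps a treated subject in follow-up for 12 months if ineligibility comes to light after the procedure. The mITT set is everyone with a scalp incision (protocol 14.3.2, SAP 7.1.3.2).

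**Missing values (SAP 7.4.1).** Missing primary and testable secondary efficacy values are multiply imputed. The listed model variables are age, sex, race and duration of disease.

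**The concern.** In a drug trial, withdrawal can at least be confused with stopping treatment. Here the treatment is one ablation, and the documents give no reason why a refused second procedure, or poor compliance, should end observation of the first.

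The 7.17 exit is also linked to outcome. Only subjects who did not reach Engel Class I, or whose procedure was incomplete, can be reviewed for retreatment, so only they can be withdrawn after a refusal. Their 12-month cognitive and quality-of-life values then go missing. The listed imputation variables carry no post-procedure seizure outcome and no reason for exit, so these subjects would be imputed largely as if they resembled those who stayed. Adverse events that begin or worsen after exit are not seen. Most of this loss is avoidable, because the visits are already scheduled.

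**Working it through.** **1. The contradiction.** Take a subject whose procedure is aborted after skin incision.

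| Step | Section | Consequence |
|---|---|---|
| May be considered for retreatment | 7.14, referring to 7.17 | Goes to the committee |
| Committee declines, so no further procedure is planned | 7.14 | Follow-up for seizures and adverse events is required |
| Same refusal | 7.17 | Withdrawal is permitted |
| Withdrawn | 7.19 | No further data |

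The two sections give this subject opposite treatment and must be reconciled.

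**2. What exit does to each endpoint.**

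- *Primary efficacy.* The window is day 30 to day 365 (protocol 14.5, SAP 7.9.2). Class IC needs two years free of disabling seizures (Appendix C), so it cannot rescue a subject at 12 months. Apart from the Class ID exception for convulsions on AED discontinuation, a disabling seizure recorded after day 30 already settles the outcome as failure, and pre-exit data are used. Only subjects who exit before such a record are exposed.
- *Secondary endpoints 3 to 7.* Each needs a 12-month score. Nothing recorded before exit replaces it, so it is imputed.
- *Primary safety.* The window runs through 12 months. A reportable event still unresolved at exit counts as permanent (Table 6 and section 10.2.3), so exit does not hide ongoing events. What is lost is new onset or worsening after exit.

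**3. The plan's own figure.** Inputs from SAP section 6: n = 150, threshold 43%, expected rate 56%, exact two-sided 95% interval.

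- The pass mark is the smallest x whose lower limit, the 0.025 quantile of Beta(x, 150 − x + 1), exceeds 0.43. For x = 76 the limit is 0.4239; for x = 77 it is 0.4305. So 77 of 150 (51.3%) are needed.
- Power = P(X ≥ 77 | 150, 0.56) = 0.891, which reproduces the stated 89%. One-tail alpha at 43% is 0.0244.

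The point disputes no stated figure. If treated subjects stay in follow-up, these values hold.

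**4. Scale of the loss under an assumption.** The documents give no exit rate. Assume 3 to 8 of 150 treated subjects leave by these routes.

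- Share of 12-month values lost: 3/150 = 2.0% to 8/150 = 5.3%. If only 90 of 150 contribute English-language scores (the 40% Spanish enrolment cap applied to treated subjects) and all leavers are among them: 3/90 = 3.3% to 8/90 = 8.9%.
- Bias in a mean change = share lost × (mean of stayers − mean of leavers). If that gap were a full Boston Naming margin of 5 points, the bias would be 0.020 × 5 = 0.10 to 0.089 × 5 = 0.44 points against a margin of 5.
- Safety, with 150 treated subjects as denominator: 47 subjects with a qualifying event pass (exact upper limit 39.4%) and 48 fail (40.1%). An unseen event in all 8 leavers would be 8/150 = 5.3 points.

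**The case against.** **What stands.** Withdrawal is optional, continuation is listed first in 7.17, and 7.19 urges subjects to stay as long as possible. Poor compliance is not poor response: the SAP's visible definition of non-compliance concerns insufficient diary information (7.1.3.2). The outcome link is therefore firm only for 7.17. The rule that unresolved events count as permanent limits the safety loss. The SAP numbering moves from 7.4.1 to 7.4.3, so further missing-data methods may exist in text not available here.

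**A stronger reading that does not hold.** A reader might infer that withdrawals inflate the primary efficacy result. If failures became missing and were imputed at the rate of the rest, then at a true 43% (64.5 expected successes) removing 3 to 8 failures would move the estimate to 64.5/147 = 43.9% to 64.5/142 = 45.4%. In a simulation of 20,000 trials with each failure missing with probability 5% (about 4 subjects), ten imputations at the observed rate and Rubin pooling, the chance of success rose from 0.025 to about 0.052. But this assumes that every such failure is treated as missing. Failures with a recorded disabling seizure after day 30 need no imputation, and the documents give no count of those who exit before one. The figures show an adverse case, not an expected effect.

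**The confounding-study exit.** Section 7.19 also names this ground: "the subject enrolls in a confounding investigational study, the subject fails to maintain adequate study compliance". A reader might want it removed too. Keeping such subjects in efficacy follow-up without an outcome rule could credit another therapy's effect to the ablation. Section 7.17 avoids that for retreatment and open resection by counting them as primary failures.

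**Conclusion.** The point holds in limited form. A treated subject can be dropped after a refused retreatment or for poor compliance, all data then stop, and nothing in the treatment requires it. The 7.17 route selects Engel I failures and incomplete procedures, and for aborted procedures it contradicts 7.14.

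The loss falls on endpoints 3 to 7 and on adverse events arising or worsening after exit. Under the assumed 3 to 8 leavers it is 2.0% to 5.3% of treated subjects, which is small against the cognitive margins but linked to outcome and avoidable. The effect on primary efficacy cannot be quantified from the documents and is confined to exits before a failing seizure is recorded. The documents do not show that the trial's primary conclusion is at risk.

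**What to change.** 1. **Protocol 7.17:** delete the sentence allowing withdrawal after a declined retreatment. This also removes the conflict with 7.14.
2. **Protocol 7.19:** state that after scalp incision a declined retreatment or poor compliance is recorded but does not end follow-up. Follow-up continues to Visit 4, by telephone under 7.15.5 if needed, unless consent is withdrawn, the subject is lost or dies, or the existing medical-necessity or best-interest ground applies.
3. **SAP 7.4.1:** state that a subject with a recorded disabling seizure after day 30, other than one covered by Class ID, is a primary failure and is not imputed.
4. **Confounding study:** leave this exit ground as it is, or keep such subjects in safety follow-up only, with a stated efficacy outcome rule.

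The cost is a protocol wording change and one SAP sentence. A few less compliant subjects would be followed to 12 months, using visits already planned. Telephone contact covers adverse events, the seizure diary and medication changes but not the cognitive tests, so some endpoint 3 to 7 values would still be missing.
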